#### REPORTING PROCEDURES

All adverse events should be reported to the trial management committee via the CI and via the trust datix system.

Depending on the nature of the event the reporting procedures below should be followed.

Any questions concerning adverse event reporting should be directed to the Chief Investigator in the first instance.

#### *Adverse Events (AE)*

All such events, whether expected or not, should be recorded.

#### *Serious Adverse Events (SAE)*

An SAE form should be completed and faxed to the Chief Investigator within 24 hours.

All SAEs should be reported to the Sponsor where in the opinion of the Chief Investigator, the event was:

- 'related', ie resulted from the administration of any of the research procedures; and
- 'unexpected', ie an event that is not listed in the protocol as an expected occurrence

Reports of related and unexpected SAEs should be submitted within 15 days of the Chief Investigator becoming aware of the event, using the NRES SAE form for non-IMP studies.

Local investigators should report any SAEs as required by their Local Research Ethics Committee, Sponsor and/or Research & Development Office.

In the event of any harm to participants in the trial, Imperial College holds Public Liability ("negligent harm") and Clinical Trial ("non-negligent harm") insurance policies, which apply to this trial. All issues will be reviewed by the TMC (AHD/CB/KD/RB), [name] (Professor of Vascular Surgery) will be available as an independent advisor.

#### **COST ESTIMATION**

The estimated duration of the study is 2 years. We anticipate recruiting about 416 patients for the one stop vein clinic and, also patients who decline the one stop clinic and prefer to attend a clinic on the normal care pathway.

The salary contributions for the CI (AHD) has been calculated at 0.05 FTE to represent the increased responsibility and anticipated time commitment from the trial co-ordinating institution (Imperial College London).

The salary contribution for CB, KS, TRAL, KD and RB has been calculated at 2% FTE.

The salary of a research nurse has been included (1 FTE).

The cost for a health economist, statistician and primary care physician has been also been included.

Other costs include cost of the questionnaires, trial registration, consumables and for dissemination of the results at conferences.

#### **CONFLICT OF INTEREST**

Most of the clinical applicants have an extensive experience of treating superficial venous reflux using multiple endovenous interventions. Some of the applicants have extensive endovenous research programmes that attract research funding. Most of the applicants have given invited lectures at meetings and many of the organisers of such events will have received industrial sponsorship. However, as the intervention being evaluated in this study is a change in the service provision in varicose vein management, we do not believe that these personal interests represent a conflict of interest in this study.

#### **regulatory issues**

##### *Ethics approval*

The Chief Investigator has obtained approval from the National Research Ethics Service (NRES) Committee (REC Ref.: 14/LO/1295). The study must be submitted for Site Specific Assessment (SSA) at each participating NHS Trust. The Chief Investigator will require a copy of the Trust R&D approval letter before accepting participants into the study. The study will be conducted in accordance with the recommendations for physicians involved in research on human subjects adopted by the 18th World Medical Assembly, Helsinki 1964 and later revisions.

##### *Consent*

Consent to enter the study will be sought from each participant only after a full explanation has been given, an information leaflet offered and time allowed for consideration. Signed participant consent will be obtained. The right of the participant to refuse to participate without giving reasons will be respected. After the participant has entered the study the clinician remains free to give alternative treatment to that specified in the protocol at any stage if he/she feels it is in the participant's best interest, but the reasons for doing so should be recorded. In these cases the participants remain within the study for the purposes of follow-up and data analysis. All participants are free to withdraw at any time from the protocol treatment without giving reasons and without prejudicing further treatment.

*Confidentiality*

The Chief Investigator will preserve the confidentiality of participants taking part in the study and is registered under the Data Protection Act.

*Indemnity*

Imperial College London holds negligent harm and non-negligent harm insurance policies which apply to this study/ Imperial College Healthcare NHS Trust holds standard NHS Hospital Indemnity and insurance cover with NHS Litigation Authority for NHS Trusts in England, which apply to this study (delete as applicable)

*Sponsor*

Imperial College London will act as the main Sponsor for this study. Delegated responsibilities will be assigned to the NHS trusts taking part in this study.

*Funding*

Partial funding for the study has been provided by the Graham-Dixon Charitable Trust.

*Audits*

The study may be subject to inspection and audit by Imperial College London under their remit as sponsor and other regulatory bodies to ensure adherence to GCP and the NHS Research Governance Framework for Health and Social Care (2nd edition).

Patient with varicose vein

GP Referral

Varicose Vein Treatment

Outpatient Clinic

Venous Duplex Scan

Outpatient clinic

Normal Care Pathway

Same day outpatient clinic, venous duplex scan and varicose vein treatment

One Stop Vein Clinic  
Not suitable for One Stop Vein Clinic  
Normal Care Pathway  
(off-trial)  
Suitable for One Stop Vein Clinic  
Letter Screening  
Randomisation

Day of Treatment:

- Picker questionnaire
- AVVQ, CIVIQ and EQ-5D
- CEAP and VCSS
- Patients given diary card to fill

Follow-up at 3 months:

- Picker questionnaire
- AVVQ, CIVIQ and EQ-5D
- CEAP and VCSS

Day of Treatment:

- Picker questionnaire
- AVVQ, CIVIQ and EQ-5D
- CEAP and VCSS
- Patients given diary card to fill

Day of Treatment:

- Picker questionnaire
- AVVQ, CIVIQ and EQ-5D
- CEAP and VCSS
- Patients given diary card to fill

Follow-up at 3 months:

- Picker questionnaire
- AVVQ, CIVIQ and EQ-5D
- CEAP and VCSS

**APPENDIX 1: Quality of Life Questionnaire**

**EQ-5D Questionnaire**

Under each heading, please tick the ONE box that best describes your health TODAY.

## 1. MOBILITY

- I have no problems in walking about
- I have slight problems in walking about
- I have moderate problems in walking about
- I have severe problems in walking about
- I am unable to walk about

## 2. SELF-CARE

- I have no problems washing or dressing myself
- I have slight problems washing or dressing myself
- I have moderate problems washing or dressing myself
- I have severe problems washing or dressing myself
- I am unable to wash or dress myself

## 3. USUAL ACTIVITIES (e.g. work, study, housework, family or leisure activities)

- I have no problems doing my usual activities
- I have slight problems doing my usual activities
- I have moderate problems doing my usual activities
- I have severe problems doing my usual activities
- I am unable to do my usual activities

## 4. PAIN/DISCOMFORT

- I have no pain or discomfort
- I have slight pain or discomfort
- I have moderate pain or discomfort
- I have severe pain or discomfort
- I have extreme pain or discomfort

## 5. ANXIETY/DEPRESSION

- I am not anxious or depressed
- I am slightly anxious or depressed
- I am moderately anxious or depressed
- I am severely anxious or depressed
- I am extremely anxious or depressed

## Appendix 2: Aberdeen Varicose Vein Questionnaire

### YOUR VARICOSE VEINS

**1. Please draw in your varicose veins in the diagram(s) below:-**

Legs viewed  
from front

Legs viewed  
from back

**2. In the last two weeks, for how many days did your varicose veins cause you pain or ache?**  
*(Please tick one box for each leg)*

R Leg

L Leg

None at all

Between 1 and 5 days

Between 6 and 10 days

For more than 10 days

**3. During the last two weeks, on how many days did you take painkilling tablets for your varicose veins?**  
*(Please tick one box for each leg)*

R Leg

L Leg

None at all

Between 1 and 5 days

Between 6 and 10 days

For more than 10 days

**4. In the last two weeks, how much ankle swelling have you had?**

*(Please tick one box)*

None at all

Slight ankle swelling

Moderate ankle swelling (eg. causing you to sit with your feet up whenever possible)

Severe ankle swelling (eg. causing you difficulty putting on your shoes)

**5. In the last two weeks, have you worn support stockings or tights?**

*(Please tick one box for each leg)*

R Leg

L Leg

No

Yes, those I bought myself without a doctor's prescription

Yes, those my doctor prescribed for me which I wear occasionally

Yes, those my doctor prescribed for me which I wear every day

**6. In the last two weeks, have you had any itching in association with your varicose veins?**

*(Please tick one box for each leg)*

R Leg  
L Leg

No

Yes, but only above the knee

Yes, but only below the knee

Both above and below the knee

**7. Do you have purple discolouration caused by tiny blood vessels in the skin, in association with your varicose veins?**

*(Please tick one box for each leg)*

R Leg  
L Leg

No

Yes

**8. Do you have a rash or eczema in the area of your ankle?**

*(Please tick one box for each leg)*

R Leg  
L Leg

No

Yes, but it does not require any treatment from a doctor or district nurse

Yes, and it requires treatment from my doctor or district nurse

**9. Do you have a skin ulcer associated with your varicose veins?**

*(Please tick one box for each leg)*

R Leg

L Leg

No

Yes

**10. Does the appearance of your varicose veins cause you concern?**

*(Please tick one box)*

No

Yes, their appearance causes me slight concern

Yes, their appearance causes me moderate concern

Yes, their appearance causes me a great deal of concern

**11. Does the appearance of your varicose veins influence your choice of clothing including tights?**

*(Please tick one box)*

No

Occasionally

Often

Always

**12. During the last two weeks, have your varicose veins interfered with your work/ housework or other daily activities?**

*(Please tick one box)*

No

I have been able to work but my work has suffered to a slight extent

I have been able to work but my work

has suffered to a moderate extent

My veins have prevented me from  
working one day or more

**13. During the last two weeks, have your varicose veins  
interfered with your leisure activities (including sport,  
hobbies and social life)?**

*(Please tick one box)*

No

Yes, my enjoyment has suffered  
to a slight extent

Yes, my enjoyment has suffered  
to a moderate extent

Yes, my veins have prevented me taking  
part in any leisure activities

### **Appendix 3. Societal Questions**

The following questions is to try assess the possible impact on society of patients having to take time off work or caring duties to attend a varicose vein appointment.

**What is your total family income?**

**What is your highest level of education attained?**

- Less than £20,000
- £20,000 - £39,999
- £40,000 - £59,999
- £60,000 - £99,999
- £100,000 and over
  
- None
- Primary education
- Secondary education
- Tertiary education

- Post-graduate degree

- Did you need to take time off work to attend your varicose vein appointment?

Yes  No (Go to Question 3)

- Did you have to take half a day or full day off?

Half-day  Full day

- What is your hourly rate of pay at work?

.....

- Do you have care commitments (e.g., children or relatives)?

Yes  No

- Did you have to ask someone to look after your child/relative so you could attend your appointment?

Yes  No

- Who did you ask?

.....

- How much did you have to pay them?

.....

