### **Secondary Outcome**

- Patient satisfaction with the service provided using the Picker patient experience questionnaire both post-operatively and at the 3 months follow-up (One Stop Vein Clinic versus Normal Care Pathway)
- Measure and compare the quality of life scores using EQ-5D, AVVQ and CIVIQ at 0 and 3 months in patients randomised to treatment in the One Stop Vein Clinic with patients randomised to the Normal Care Pathway
- Time from referral to treatment
- Assess the cost-effectiveness of the One Stop Vein clinic compared to the normal care pathway
- Record the time to return to normal activities and to work
- Assess the estimated societal costs

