#### **Estimated societal costs.**

Data will be collected on time off from work and carer's duties (child/relative/friend). Additionally, data on income, cost of attending clinic and impact on family and colleagues will be assessed to estimate the societal cost of the two pathways.

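### The societal-cost form asks no duration for replacement care, so time off caring duties is not directly measured and unpaid cover is recorded as £0 unless hours and a value are imputed

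*Protocol*

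**What the plan says.** Societal cost appears among the secondary outcomes: "Assess the estimated societal costs". The Protocol section on estimated societal costs sets out what will be gathered: "Data will be collected on time off from work and carer's duties (child/relative/friend". It adds that "impact on family and colleagues will be assessed to estimate the societal cost of the two pathways". The introduction to Appendix 3 gives the purpose of its questions as the effect on society of "patients having to take time off work or caring duties to attend a varicose vein appointment".

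Appendix 3 then has four care items: whether the patient has care commitments (yes/no); "Did you have to ask someone to look after your child/relative so you could attend your appointment" (yes/no); "Who did you ask" (free text); and "How much did you have to pay them" (free text). None asks how long the cover lasted, and none asks whether the stand-in gave up paid work.

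For work, the same form asks whether time off was needed, whether it was a half or a full day, and the hourly rate of pay.

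**The concern.** A time cost needs a quantity and a price. For work the form collects both. For care it collects a price only when money changed hands, and it never collects a quantity. One of the two kinds of lost time that the form names is therefore not directly measured.

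This bears on the comparison because the two pathways differ mainly in how often, and for how long, patients must attend. Care hours follow attendance. If they are not recorded, the care part of the societal-cost difference between arms has to come from assumptions. An analysis plan can fix a unit value for unpaid care afterwards, but it cannot recover hours that were never asked. How often the form is completed is a separate matter: repeating it at every visit would still yield no duration.

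**Working it through.** The protocol states no figure for carer time, so there is nothing to reproduce. The check is a comparison of items, followed by a sensitivity calculation on assumed hours.

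**1. Items side by side (Appendix 3)**

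| | Needed? | Duration | Price |
|---|---|---|---|
| Time off work | yes/no | half or full day | hourly pay |
| Time off caring | yes/no | not asked | amount paid, if any |

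Of four care items, none has a duration and one has a quantity (money).

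**2. What the form yields, by type of patient**

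- Paid cover: the amount is known, the hours are not.
- Unpaid cover, patient took time off work: £0 paid. The half-day or full-day answer is a rough proxy for hours.
- Unpaid cover, patient took no time off work: £0 paid, and no proxy. The routing after a No to the work question must at least bypass the half-day or full-day item.

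**3. Other instruments.** The patient diary (Appendix 9) records the day of return to work and to normal activities after treatment. It does not cover care time given up to attend appointments. None of the other appendices asks about it.

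**4. Attendances.** The Background gives at least two clinics and one scan visit before the procedure: 2 + 1 + 1 = 4. The one-stop arm has 1, combining clinic, scan and treatment.

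**5. Dependence on duration.** For a patient who needs cover at every attendance:

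hours difference = (sum of normal-pathway visit hours) − (one-stop visit hours)

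The hours and the £7 to £15 per hour below are assumptions; neither is in the protocol.

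| Normal pathway | One-stop | Difference | At £7 to £15/h |
|---|---|---|---|
| 4 × 2 h = 8 h | 8 h | 0 h | £0 |
| 4 × 4 h = 16 h | 8 h | 8 h | £56 to £120 |
| 3 × 4 h + 8 h = 20 h | 8 h | 12 h | £84 to £180 |
| 4 × 8 h = 32 h | 8 h | 24 h | £168 to £360 |

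Break-even is where the average normal-pathway visit lasts a quarter of the one-stop visit; below that the sign reverses. The result is governed by the quantity that the form omits.

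**The case against.** A reader might infer that the protocol costs unpaid care at £0. It does not say so. It sets no costing rule, the payment item records only an out-of-pocket amount, and the item on who was asked lets informal cover be identified and valued. The valuation rule may sit in an analysis plan that is not shown, and a health economist is budgeted. This stands: £0 is what the payment item records, not what the analysis must use.

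A reader might also infer that carer time is impossible to estimate. That is too strong. The half-day or full-day answer is a proxy for those who took time off work, and a standard duration per type of visit could be imputed for the rest. But imputing the duration per visit supplies by assumption much of the difference that the form is there to help measure.

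Nor do the documents show that most cover is unpaid, or what it would be worth. They give no share, hours or rate, so a ratio to the £186 per patient implied by the cost-benefit section (2 × £93) would rest on assumptions. It would also compare a subgroup with all patients.

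It can be added that the societal-cost section does not name Appendix 3 as its sole source, and that it does not define family impact as a stand-in's lost paid work. Both are fair. Still, Appendix 3 states caring duties as part of its own purpose, and no other instrument in the protocol collects them. Finally, this is one secondary outcome of a pilot; the primary outcome is unaffected.

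**Conclusion.** The point holds in a limited form. Appendix 3 does not directly measure time off caring duties, which the protocol says will be assessed. Unpaid cover is recorded as £0 unless a duration and a value are imputed, and patients who took no time off work have no proxy for the duration.

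With more attendances in the normal care pathway, valuing unpaid cover at the recorded £0 would probably understate that pathway's cost more, and so understate any one-stop saving. That direction is likely, not proven, because it depends on visit lengths that the protocol does not give. The size cannot be derived from the document. The spread of 0 to 24 hours (£0 to £360) per patient relying on unpaid cover shows sensitivity to assumptions and is not an estimate of bias. The change is worth making before the form is used, because hours not asked for cannot be supplied by a later analysis.

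**What to change.** In Appendix 3, directly after the item on who was asked, add two questions: *For how many hours did they look after your child/relative?* and *Did they take time off paid work to do so?* Check that the routing brings every patient with care commitments to these items, whether or not they took time off work. Value unpaid hours the same way in both arms; the rate itself can be left to the analysis plan.

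The cost is two more questions for patients on an existing form.

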#### Appendix 4: Clinical assessment of Varicose Veins

Hospital Number-----

**MALE**

**FEMALE**

Number of Pregnancies

Weight/ Kg

BMI>30

Yes

No

OCP or HRT

Yes

No

Smoker

Yes

No

Date of birth-----

Age -----

Occupation-----  
Date-----

#### **Past Medical History**

	Yes	No		Yes	No
Bleeding disorder			IHD		
DVT/PE			Leg ulcers		
Diabetes			Hypertension		

#### **Medications**

---

---

#### **Previous treatment to Varicose Veins**

Side  
Site  
Date  
Treatment type

#### **Appendix 5: Pre Operative Clinical Assessment**

**Score**

**Definition**

**0**

**Asymptomatic**

**1**

**Symptomatic, but able to carry out usual activities with out compressive therapy**

**2**

**Able to carry out usual activities only with compressive therapy and/or limb elevation**

**3**

**Unable to carry out usual activities even with compression and/or elevation**

**Usual activities = patients activities before the onset of disability due to venous disease**

## **Appendix 6: Venous Clinical Severity Score (VCSS)**

**Please indicate right or left leg or bilateral (R, L or B)**

Absent  
Mild  
Moderate  
Severe  
Pain  
None  
Occasional, non/ no analgesia restricting  
With moderate activity, occasional analgesia  
Daily, severe limitations, regular analgesia  
Varicose veins>4mm  
None  
Few  
Multiple GSV  
Extensive GSV and LSV  
Venous oedema  
None  
Evening/ankle  
Afternoon/ above knee  
Morning/requiring elevation  
Skin pigmentation  
None  
Limited and old/brown  
Diffuse lower third/ purple  
  
Wide/ purple

Inflammation  
None  
Mild cellulitis in marginal area  
Moderate involving most of gaiter area  
Severe cellulitis or significant eczema  
Induration  
None  
Focal <5cm  
Medial or lateral less than lower 1/3  
1/3 of lower leg or more  
Number of active ulcers  
0  
1

2

3

Active ulcer duration  
None  
<3 months  
>3 months  
<12 months

>12 months  
Active ulcer diameter( cm)  
None  
<2  
2-6  
>6  
Compression  
Not used or non compliant  
Intermittent use  
Stockings worn most days  
Stockings worn daily

Total

#### **Appendix 7: Clinical-Etiology-Anatomy-Pathophysiology.(CEAP Classification)**

##### **Clinical**

0  
1A  
1S  
2A  
2S  
3A  
3S  
4aA  
4aS  
4bA  
4bS  
5A  
5S  
6

##### **Etiology**

Congenital  
Primary  
Secondary  
No venous cause identified

##### **Anatomy**

Superficial  
Deep  
Perforating  
No venous location identified

##### **Pathology**

Reflux  
Obstruction  
Both  
No venous pathology identified

Class 0 No visible or palpable veins	Class 5 Skin changes and healed ulceration
Class 1 Telangiectasia, reticular veins	Class 6 Active venous ulcers
Class 2 Varicose Veins	
Class 3 Oedema without skin changes	
Class 4 Skin changes ascribed to venous disease	A= Asymptomatic
4a) Pigmentation or eczema	S= Symptomatic
4b) Lipodermatosclerosis or atrophie blanche	

## Appendix 8. CIVIQ-14 Questionnaire

### C I V I Q-14 SELF-QUESTIONNAIRE PATIENTS *In English language for UK*

Many people complain of leg pain. We would like to find out how often these leg problems occur and to what extent they affect the everyday lives of those who suffer from them.

Below you will find a list of symptoms, sensations or types of discomfort that you may be experiencing and which may make everyday life hard to bear to a greater or lesser extent. **For each symptom, sensation, or type of discomfort listed, we would like you to answer in the following way:**

Please indicate if you have experienced what is described in each sentence, and if the answer is 'yes', how **intense** it was. There are five possible answers, and we would like you to circle the one which best describes your situation.

Circle 1 if you feel the symptom, sensation or discomfort described does not apply to you

•  
•  
•  
•  
•  
C  
i  
r  
c  
i  
e  
2  
,3  
,,

i  
f  
y  
c  
u  
h  
a  
v  
e  
f  
e  
l  
i  
t  
i  
t  
c  
a  
g  
r  
e  
a  
t  
e  
r  
c  
r  
i  
e  
s  
s  
e  
r  
e  
x  
t  
e  
n

•  
•  
•

